9.6.4.5 Other Safety Variables

Urine pregnancy results will be listed.

9.7 Pharmacokinetic Analysis

A listing of the PK data, including buprenorphine and norbuprenorphine plasma concentration measurement, will be provided. The population PK analysis of the drug plasma concentration data will be reported separately.

10.0 Validation

PRA's goal is to ensure that each TFL delivery is submitted to the highest level of quality. Our quality control procedures will be documented separately in the study specific quality control plan.

Appendix 1 Glossary of Abbreviations

Glossary of Abbreviations:	
ADY	Analysis Day
AE	Adverse event
ALP	Alkaline Phosphatase
ALT	Alanine Aminotransferase
AST	Aspartate Aminotransferase
BMI	Body Mass Index
CDF	Cumulative Distribution Function
CRF	Case Report Form
COWS	Clinical Opioid Withdrawal Scale
CTMS	Clinical Trials Management System
eC-SSRS	Electronic Columbia Suicide Severity Rating Scale
ECG	Electrocardiogram
EOS	End of Study
ET	Early Termination
IA	Interim Analysis
IDC	Individual Drug Counseling
MedDRA	Medical Dictionary for Regulatory Activities
PDV	Protocol Deviation
PK	Pharmacokinetic
PT	Preferred Term
RBP	Reckitt Benckiser Pharmaceuticals Inc.
SAP	Statistical Analysis Plan
SAE	Serious Adverse Event
SC	Subcutaneous
SD	Standard Deviation
SDTM	Study Data Tabulation Model
SDTMIG	Study Data Tabulation Model Implementation Guide
SI	International System
SOC	System Organ Class
SOWS	Subjective Opioid Withdrawal Scale
TEAE	Treatment-Emergent Adverse Event
TLFB	Timeline Followback

Sponsor: Indivior Inc.
Protocol no: RB-US-13-0003

TFLs	Tables, Listings, and Figures
UDS	Urine Drug Screen
ULN	Upper Limit of Normal
VAS	Visual Analog Scale
WHODRUG	World Health Organization Drug Dictionary

Sponsor: Indivior Inc.
 Protocol no: RB-US-13-0003

Appendix 2 List of Preferred Terms from Standard MedDRA Queries for Adverse Events of Special Interest

Adverse Events Potentially Pertaining to Pancreatitis

Preferred Terms Potentially Pertaining to Pancreatitis		
Amylase abnormal	Hyperbilirubinaemia	Pancreatic haemorrhage
Amylase creatinine clearance ratio abnormal	Hyperlipasaemia	Pancreatic necrosis
Amylase increased	Ischaemic pancreatitis	Pancreatic phlegmon
Bilirubin conjugated abnormal	Lipase abnormal	Pancreatic pseudocyst
Blood bilirubin increased	Lipase increased	Pancreatic pseudocyst drainage
Blood trypsin increased	Lipase urine increased	Pancreatitis
Cullen's sign	Oedematous pancreatitis	Pancreatitis acute
Grey Turner's sign	Pancreatic abscess	Pancreatitis haemorrhagic
Haemorrhagic necrotic pancreatitis	Pancreatic enzyme abnormality	Pancreatitis necrotising
Hereditary pancreatitis	Pancreatic enzymes abnormal	Pancreatitis relapsing
Hyperamylasaemia	Pancreatic enzymes increased	Pancreatorenal syndrome

Adverse Events Potentially Pertaining to Respiration Depression and Failure

Preferred Terms Potentially Pertaining to Respiratory Depression and Failure		
Acute respiratory distress syndrome	Hypopnoea	Respiratory depression
Acute respiratory failure	Hypoventilation	Respiratory depth decreased
Apnoea	Hypoventilation neonatal	Respiratory distress
Apnoea neonatal	Lung hypoinflation	Respiratory failure
Infantile apnoea	Meconium aspiration syndrome	Respiratory paralysis
Apnoeic attack	Neonatal respiratory arrest	Respiratory rate decreased
Bradypnoea	Neonatal respiratory depression	Severe acute respiratory syndrome
Breath sounds absent	Neonatal respiratory distress syndrome	Cardio-respiratory arrest
Cardio-respiratory distress	Neonatal respiratory failure	Cardio-respiratory arrest neonatal
Central-alveolar hypoventilation	Respiratory arrest	Cardiopulmonary failure
Chronic respiratory failure		

Sponsor: Indivior Inc.
 Protocol no: RB-US-13-0003

Adverse Events Potentially Pertaining to Central Nervous System Depression

Preferred Terms Potentially Pertaining to Central Nervous System Depression		
Mental fatigue	Postictal state	Psychomotor seizures
Microsleep	Consciousness fluctuating	Simple partial seizures
Narcolepsy	Neonatal oversedation	Autonomic seizure
Coma	Hypoglycaemic unconsciousness	Atonic seizures
Impaired driving ability	Hyperglycaemic unconsciousness	Seizure
Impaired ability to use machinery	Post-injection delirium sedation syndrome	Partial seizures with secondary generalisation
Accident	Preictal state	Alcoholic seizure
Road traffic accident	Psychogenic pseudosyncope	Partial seizures
Vision blurred	Mental status changes	Seizure like phenomena
Vertigo CNS origin	Mental status changes postoperative	Seizure cluster
Incoherent	Slow response to stimuli	Change in seizure presentation
Disturbance in attention	Unresponsive to stimuli	Migraine-triggered seizure
Judgement impaired	Hyporesponsive to stimuli	Psychogenic seizure
Mental impairment	Benign familial neonatal convulsions	Seizure anoxic
Borderline mental impairment	Febrile convulsion	Post stroke seizure
Cognitive disorder	Drug withdrawal convulsions	Accidental death
Altered state of consciousness	Convulsion neonatal	Accidental overdose
Depressed level of consciousness	Convulsions local	Accidental exposure to product
Lethargy	Tonic convulsion	Cerebrovascular accident
Loss of consciousness	Convulsion in childhood	Dizziness
Sedation	Clonic convulsion	Dizziness exertional
Somnolence	Acute encephalitis with refractory, repetitive partial seizures	Dizziness postural
Somnolence neonatal	Generalised tonic-clonic seizure	Procedural dizziness
Stupor	Complex partial seizures	Neurotoxicity
Syncope		

Adverse Events Potentially Pertaining to Orthostatic Hypotension

Preferred Terms Potentially Pertaining to Orthostatic Hypotension		
Orthostatic hypotension	Vision blurred	Dizziness
Dizziness exertional	Dizziness postural	Syncope
Presyncope	Diastolic hypotension	Hypotension

Sponsor: Indivior Inc.
 Protocol no: RB-US-13-0003

Adverse Events Potentially Pertaining to Drug Withdrawal Symptoms

Preferred Terms Potentially Pertaining to Drug Withdrawal Symptoms		
Agitation	Hypertension	Piloerection
Anxiety	Hypervigilance	Pruritus
Arthralgia	Influenza like illness	Psychomotor hyperactivity
Bone pain	Insomnia	Pyrexia
Chills	Irritability	Respiratory rate increased
Decreased appetite	Lacrimal disorder	Restlessness
Depression	Lacrimation increased	Rhinitis
Diarrhoea	Malaise	Rhinorrhoea
Dizziness	Muscle spasms	Sneezing
Drug dependence	Muscle twitching	Tachycardia
Flushing	Myalgia	Tremor
Heart rate increased	Mydriasis	Vomiting
Hyperhidrosis	Nausea	Yawning
Drug Withdrawal Syndrome		

Adverse Events Potentially Pertaining to Hepatic Events

Preferred Terms Potentially Pertaining to Hepatic Events		
Bilirubin excretion disorder	Oesophageal varices haemorrhage	Galactose elimination capacity test decreased
Cholaemia	Peripancreatic varices	Gamma-glutamyltransferase abnormal
Cholestasis	Portal fibrosis	Gamma-glutamyltransferase increased
Cholestatic liver injury	Portal hypertension	Guanase increased
Cholestatic pruritus	Portal hypertensive enteropathy	Hepaplastin abnormal
Drug-induced liver injury	Portal hypertensive gastropathy	Hepaplastin decreased
Hepatitis cholestatic	Portal vein cavernous transformation	Hepatic artery flow decreased
Hyperbilirubinaemia	Portal vein dilatation	Hepatic congestion
Icterus index increased	Portopulmonary hypertension	Hepatic enzyme abnormal
Jaundice	Renal and liver transplant	Hepatic enzyme decreased
Jaundice cholestatic	Retrograde portal vein flow	Hepatic enzyme increased
Jaundice hepatocellular	Reye's syndrome	Hepatic function abnormal
Mixed liver injury	Reynold's syndrome	Hepatic hydrothorax
Ocular icterus	Splenic varices	Hepatic hypertrophy
Parenteral nutrition associated liver disease	Splenic varices haemorrhage	Hepatic mass
Deficiency of bile secretion	Steatohepatitis	Hepatic pain
Yellow skin	Subacute hepatic failure	Hepatic sequestration
Acute hepatic failure	Varices oesophageal	Hepatic vascular resistance increased

Sponsor: Indivior Inc.

Protocol no: RB-US-13-0003

Acute on chronic liver failure	Varicose veins of abdominal wall	Hepatobiliary scan abnormal
Acute yellow liver atrophy	Anorectal varices	Hepatomegaly
Ascites	Anorectal varices haemorrhage	Hepatosplenomegaly
Asterixis	Intrahepatic portal hepatic venous fistula	Hyperammonaemia
Bacterascites	Peritoneovenous shunt	Hyperbilirubinaemia
Biliary cirrhosis	Portal shunt	Hypercholia
Biliary cirrhosis primary	Portal shunt procedure	Hypertransaminaemia
Biliary fibrosis	Small-for-size liver syndrome	Kayser-Fleischer ring
Cholestatic liver injury	Spider naevus	Liver function test abnormal
Chronic hepatic failure	Splenorenal shunt	Liver induration
Coma hepatic	Splenorenal shunt procedure	Liver palpable
Cryptogenic cirrhosis	Spontaneous intrahepatic portosystemic venous shunt	Liver scan abnormal
Diabetic hepatopathy	Stomal varices	Liver tenderness
Drug-induced liver injury	Acute graft versus host disease in liver	Mitochondrial aspartate aminotransferase increased
Duodenal varices	Allergic hepatitis	Molar ratio of total branched-chain amino acid to tyrosine
Gallbladder varices	Autoimmune hepatitis	Oedema due to hepatic disease
Gastric variceal injection	Chronic graft versus host disease in liver	Perihepatic discomfort
Gastric variceal ligation	Chronic hepatitis	Retrograde portal vein flow
Gastric varices	Graft versus host disease in liver	Total bile acids increased
Gastric varices haemorrhage	Hepatitis	Transaminases abnormal
Hepatectomy	Hepatitis acute	Transaminases increased
Hepatic atrophy	Hepatitis cholestatic	Ultrasound liver abnormal
Hepatic calcification	Hepatitis chronic active	Urine bilirubin increased
Hepatic cirrhosis	Hepatitis chronic persistent	X-ray hepatobiliary abnormal
Hepatic encephalopathy	Hepatitis fulminant	5'nucleotidase increased
Hepatic encephalopathy prophylaxis	Hepatitis toxic	Blood alkaline phosphatase abnormal
Hepatic failure	Ischaemic hepatitis	Blood alkaline phosphatase increased
Hepatic fibrosis	Lupus hepatitis	Blood cholinesterase abnormal
Hepatic hydrothorax	Non-alcoholic steatohepatitis	Blood cholinesterase decreased
Hepatic infiltration eosinophilic	Radiation hepatitis	Deficiency of bile secretion
Hepatic lesion	Steatohepatitis	Glutamate dehydrogenase increased
Hepatic necrosis	Granulomatous liver disease	Haemorrhagic ascites
Hepatic steato-fibrosis	Liver sarcoidosis	Hepatic fibrosis marker abnormal
Hepatic steatosis	Portal tract inflammation	Hepatic fibrosis marker increased
Hepatitis fulminant	Alanine aminotransferase abnormal	Hypoalbuminaemia
Hepatobiliary disease	Alanine aminotransferase increased	Leucine aminopeptidase increased
Hepatocellular foamy cell syndrome	Ammonia abnormal	Liver function test decreased
Hepatocellular injury	Ammonia increased	Liver function test increased

Sponsor: Indivior Inc.
 Protocol no: RB-US-13-0003

Hepatopulmonary syndrome	Ascites	Liver iron concentration abnormal
Hepatorenal failure	Aspartate aminotransferase abnormal	Liver iron concentration increased
Hepatorenal syndrome	Aspartate aminotransferase increased	Model for end stage liver disease score abnormal
Hepatotoxicity	Bacterascites	Model for end stage liver disease score increased
Intestinal varices	Bile output abnormal	Periportal oedema
Intestinal varices haemorrhage	Bile output decreased	Peritoneal fluid protein abnormal
Liver and small intestine transplant	Biliary ascites	Peritoneal fluid protein decreased
Liver dialysis	Bilirubin conjugated abnormal	Peritoneal fluid protein increased
Liver disorder	Bilirubin conjugated increased	Pneumobilia
Liver injury	Bilirubin urine present	Portal vein flow decreased
Liver operation	Biopsy liver abnormal	Portal vein pressure increased
Liver transplant	Blood bilirubin abnormal	Retinol binding protein decreased
Lupoid hepatic cirrhosis	Blood bilirubin increased	Urobilinogen urine decreased
Minimal hepatic encephalopathy	Blood bilirubin unconjugated increased	Urobilinogen urine increased
Mixed liver injury	Bromosulphthalein test abnormal	Alcoholic liver disease
Nodular regenerative hyperplasia	Child-Pugh-Turcotte score abnormal	Cirrhosis alcoholic
Non-alcoholic fatty liver	Child-Pugh-Turcotte score increased	Fatty liver alcoholic
Non-alcoholic steatohepatitis	Computerised tomogram liver	Hepatic steato-fibrosis
Non-cirrhotic portal hypertension	Foetor hepaticus	Hepatitis alcoholic
Oedema due to hepatic disease	Galactose elimination capacity test abnormal	Zieve syndrome

Sponsor: Indivior Inc.
 Protocol no: RB-US-13-0003

Adverse Events Potentially Pertaining to Injection Site Reactions

Preferred Terms Potentially Pertaining to Injection Site Reactions		
Immediate post-injection reaction	Injection site irritation	Injection site movement impairment
Injection related reaction	Injection site mass	Injection site lymphadenopathy
Injection site abscess	Injection site necrosis	Injection site nodule
Injection site cellulitis	Injection site nerve damage	Embolia cutis medicamentosa
Injection site infection	Injection site oedema	Injection site scar
Injection site pustule	Injection site pain	Injection site discharge
Injection site abscess sterile	Injection site paraesthesia	Injection site pallor
Injection site anaesthesia	Injection site phlebitis	Injection site papule
Injection site atrophy	Injection site pruritus	Injection site injury
Injection site bruising	Injection site rash	Injection site scab
Injection site cyst	Injection site reaction	Injection site eczema
Injection site dermatitis	Injection site thrombosis	Injection site streaking
Injection site erosion	Injection site ulcer	Injection site dryness
Injection site erythema	Injection site urticaria	Injection site laceration
Injection site extravasation	Injection site vesicles	Injection site macule
Injection site fibrosis	Injection site warmth	Injection site vasculitis
Injection site granuloma	Injection site ischaemia	Injection site exfoliation
Injection site haematoma	Injection site coldness	Injection site dysaesthesia
Injection site haemorrhage	Injection site discolouration	Injection site plaque
Injection site hypersensitivity	Injection site photosensitivity reaction	Injection site hyperaesthesia
Injection site hypertrophy	Injection site swelling	Injection site hypoaesthesia
Injection site induration	Injection site discomfort	Injection site hypertrichosis
Injection site inflammation	Injection site calcification	

Sponsor: Indivior Inc.
Protocol no: RB-US-13-0003

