#### 1.4.2 Summary of Previous Clinical Data

In the first-in-human trial to evaluate the safety, tolerability, and PK of RBP-6000, 12 subjects received a single SC injection of RBP-6000 containing 20 mg of buprenorphine. Of these 12 subjects, 6 subjects completed the study through Day 85. The majority (94%) of treatment-emergent adverse events (TEAEs) were mild, 5.4% were moderate, and 1 was severe in intensity. TEAEs considered related to the study drug included injection site pain, injection site warmth, and injection site bruising, erythema, and edema. All subjects experienced mild to moderate symptoms of withdrawal at study entry, prior to study drug injection, and after study drug injection. One serious adverse event (SAE) was reported. The SAE was notably identified psychosocial stressors and intermittent withdrawal, for which the subject had prolonged hospitalization for treatment. This SAE was not considered to be related to the study drug. No respiratory depression, temperature elevations, clinically significant lowering of oxygen saturation, or electrocardiogram (ECG) abnormalities were observed. There was 1 clinically significant laboratory adverse event (AE; elevated hepatic enzymes), which resolved. No unexpected side effects occurred in the RBP-6000 depot formulation of buprenorphine (RBP-6000 IB, Edition 4, 24 February 2014). Buprenorphine was rapidly absorbed over the first day and peaked on the second day, with a slow decrease in plasma concentrations thereafter that is consistent with the slow release of buprenorphine from the ATRIGEL Delivery System.

The PK of 50, 100, and 200 mg buprenorphine (as RBP-6000) was also evaluated in a single-ascending-dose study in 51 subjects (RB-US-11-0020). In this study, median buprenorphine time to peak concentration ( $t_{max}$ ) in the initial burst period was observed at 24 hours for all 3 dosages. Buprenorphine mean plasma terminal half-life increased slightly with the increase in dose from 50 mg to 200 mg (1078 hours [44.9 days] at 50 mg, 1376 hours at 100 mg, and 1573 hours at 200 mg). Buprenorphine exhibited overall geometric mean average concentration values of 0.356, 0.624, and 1.108 ng/mL, respectively with 50, 100 and 200 mg buprenorphine while overall geometric mean  $C_{max}$  values of 0.999, 1.518, and 2.381 ng/mL were observed for buprenorphine doses of 50, 100, and 200 mg, respectively. With an increase in dose of RBP-

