## 6.4 Vital Signs

Evaluation of vital signs will be performed after the subject has been supine for  $\geq 3$  minutes and will include a measurement of systolic and diastolic BP, pulse rate, pulse oximetry, respiratory rate, and oral temperature.

If clinically significant findings, as determined by the Investigator or medically qualified sub-investigator, occur in any vital sign measurement, that measurement will be captured as an AE and repeated at medically appropriate intervals until the value returns to an acceptable range, a specific diagnosis is established, or the condition is otherwise explained.

Assessments will be recorded in the source documents and eCRF and will be performed at the time points detailed in the SOE ([Appendix 1](#), [Appendix 2](#), [Appendix 3](#), [Appendix 4](#), and [Appendix 5](#)).

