## Appendix 12 Clinical Opiate Withdrawal Scale (COWS)

For each item, mark the choice that best describes the subject's signs or symptom. Rate on just the apparent relationship to opiate withdrawal. For example, if heart rate is increased because the patient was jogging just prior to assessment, the increased pulse rate would not add to the score.

**1. Resting Pulse Rate:** *Measured after patient is sitting or lying for one minute.*

- \_\_\_\_\_ beats/min
- 0 - Pulse rate 80 or below
  - 1 - Pulse rate 81 - 100
  - 2 - Pulse rate 101 - 120
  - 4 - Pulse rate greater than 120

**2. GI upset:** *Over last 1/2 hour.*

- 0 - No GI symptoms
- 1 - Stomach cramps
- 2 - Nausea or loose stool
- 3 - Vomiting or diarrhea
- 5 - Multiple episodes of diarrhea or vomiting

**3. Sweating:** *Over past 1/2 hour not accounted for by room temperature or patient activity.*

- 0 - No report of chills or flushing
- 1 - Subjective report of chills or flushing
- 2 - Flushed or observable moistness on face
- 3 - Beads of sweat on brow or face
- 4 - Sweat streaming off face

**4. Tremor:** *Observation of outstretched hands.*

- 0 - No tremor
- 1 - Tremor can be felt, but not observed
- 2 - Slight tremor observable
- 4 - Gross tremor or muscle twitching

**5. Restlessness:** *Observation during assessment.*

- 0 - Able to sit still
- 1 - Reports difficulty sitting still, but is able to do so
- 3 - Frequent shifting or extraneous movements of legs/arms
- 5 - Unable to sit still for more than a few seconds

**6. Yawning:** *Observation during assessment.*

- 0 - No yawning
- 1 - Yawning once or twice during assessment
- 2 - Yawning three or more times during assessment
- 4 - Yawning several times/minute

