## Appendix 13 Subjective Opiate Withdrawal Scale (SOWS)

		PLEASE SCORE EACH OF THE 16 ITEMS BELOW ACCORDING TO HOW YOU FEEL NOW (CIRCLE ONE NUMBER)				
	SYMPTOM	NOT AT ALL	A LITTLE	MODERATELY	QUITE A BIT	EXTREMELY
1	I feel anxious	0	1	2	3	4
2	I feel like yawning	0	1	2	3	4
3	I am perspiring	0	1	2	3	4
4	My eyes are teary	0	1	2	3	4
5	My nose is running	0	1	2	3	4
6	I have goosebumps	0	1	2	3	4
7	I am shaking	0	1	2	3	4
8	I have hot flushes	0	1	2	3	4
9	I have cold flushes	0	1	2	3	4
10	My bones and muscles ache	0	1	2	3	4
11	I feel restless	0	1	2	3	4
12	I feel nauseous	0	1	2	3	4
13	I feel like vomiting	0	1	2	3	4
14	My muscles twitch	0	1	2	3	4
15	I have stomach cramps	0	1	2	3	4
16	I feel like using now	0	1	2	3	4

Modified from : Handelsman L, Cochrane KJ, Aronson MJ, Ness R, Rubenstein KJ, Kanof PD (1987). Two new rating scales for opiate withdrawal. *Am J Drug Alcohol Abuse* 13:293-308.

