9.6.1.9 Potentially Pertaining to Respiratory Depression and Failure

A summary of TEAEs potentially pertaining to respiratory depression and failure, as defined in [Appendix 2](#), will be summarized by SOC and PT for the Safety Analysis Set.

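### The SAP's respiratory-depression term list has no oxygen-desaturation or hypoxia term, so the special-interest table can miss events that the trial's own pulse oximetry may produce

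*SAP*

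**What the plan says.** SAP 9.6.1.9 plans "A summary of TEAEs potentially pertaining to respiratory depression and failure, as defined in" Appendix 2, by SOC and preferred term in the Safety Analysis Set. Whether an event enters this table thus depends only on whether its preferred term is on the list headed "Preferred Terms Potentially Pertaining to Respiratory Depression and Failure". Appendix 2 gives its overall source as a "List of Preferred Terms from Standard MedDRA Queries for Adverse Events of Special Interest", but does not name the queries, their scope or any rule for selecting terms.

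Protocol 6.4 includes pulse oximetry in the vital signs. When findings that the investigator or a qualified sub-investigator judges clinically significant "occur in any vital sign measurement, that measurement will be captured as an AE". Under the schedules of events, vital signs are taken before and after every injection.

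Two other outputs bear on the point. SAP 9.6.1.1 tabulates all TEAEs by SOC and preferred term, counting each subject once per term, with coding in MedDRA 17.1. SAP 9.6.3 gives descriptive statistics for pulse oximetry by visit and time point, with change from baseline, and a separate listing.

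**The concern.** Long-term safety is the primary objective, and the product is a depot opioid: Protocol 1.4.2 reports mean terminal half-lives of 1078 to 1573 hours after single doses of 50 to 200 mg. A reader who wants to know how many subjects had respiratory depression will look at the 9.6.1.9 table first, because no other planned output groups such events. Low saturation is one way this trial could detect the problem. The sponsor's own summary of the first-in-human study (Protocol 1.4.2) names "clinically significant lowering of oxygen saturation" next to respiratory depression, reporting that neither was observed. If a desaturation recorded as an adverse event cannot enter the table, a low count there is harder to trust.

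**Working it through.** The plan states no figure on this point, so the check compares the list with the protocol's measurements.

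**1. Count the list.** SAP Appendix 2 gives 31 respiratory terms. Nine are neonatal or infant terms: *Hypoventilation neonatal*, *Apnoea neonatal*, *Infantile apnoea*, *Meconium aspiration syndrome*, *Neonatal respiratory arrest*, *Neonatal respiratory depression*, *Neonatal respiratory distress syndrome*, *Neonatal respiratory failure* and *Cardio-respiratory arrest neonatal*. De novo subjects must be 18 to 65 (Protocol 4.2), and the lowest age band in SAP 9.3 starts at 18. That leaves 31 − 9 = 22 terms that could be reported here.

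**2. Search it.** No term contains oxygen, saturation, hypoxia, cyanosis or oximetry: 0 of 31.

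**3. Compare with the list's own logic.** The respiratory list already accepts a term that is a vital-sign reading, *Respiratory rate decreased*. Other Appendix 2 lists accept measurement terms too, such as *Heart rate increased*, *Amylase increased* and *Alanine aminotransferase increased*. Saturation is the respiratory vital sign without a term.

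**4. Trace an event.** Suppose a low reading after an injection is judged clinically significant.
- Protocol 6.4 makes it an adverse event.
- If it is treatment-emergent and coded to a desaturation or hypoxia term, it enters the SOC and preferred-term tables of SAP 9.6.1.1 and the listings.
- It cannot enter the 9.6.1.9 table. The subject is counted there only if he or she also has a listed term.

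**5. Look for a substitute.** The SOC and preferred-term tables show the event but do not group it with respiratory depression. SAP 9.6.3 plans no count of subjects below a saturation threshold, and a few low readings among about 600 subjects would hardly move a mean. Nothing else gives the grouped count.

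**6. Size.** The documents give no rate. Let p be the assumed share of subjects whose only respiratory TEAE carries an omitted term, and take 600 subjects, the approximate planned enrolment (the Safety Analysis Set may be smaller). Subjects missed = 600 × p.

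| Assumed p | Subjects missed |
|---|---|
| 0 | 0 |
| 0.1% | 0.6 |
| 0.5% | 3 |
| 1% | 6 |
| 2% | 12 |

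Each missed subject is worth 1/600 = 0.17 percentage points. Adding terms can only raise the count or leave it unchanged.

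**The case against.** The strongest reply is that no event is lost. Every TEAE appears by SOC and preferred term, by severity and by relationship; serious events and discontinuations have their own tables; oximetry is summarised and listed. An investigator may also report a diagnosis instead of the reading, and *Respiratory depression*, *Hypoventilation*, *Hypopnoea* and *Bradypnoea* are all listed. The duty in Protocol 6.4 covers only findings judged clinically significant. All of this stands. It limits the consequence to one table, but it does not supply the grouped count.

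A second reply is that the list may be a standard query taken over whole, which would also explain the neonatal terms. Those terms add nothing to any adult count and are not a defect in themselves. Because the query and its scope are not named, the documents do not show whether desaturation terms were considered.

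A reader might extend the point to the list headed "Preferred Terms Potentially Pertaining to Drug Withdrawal Symptoms". Its 40 terms include none for abdominal pain or cramp, although SOWS asks about "I have stomach cramps" and COWS scores "1 - Stomach cramps"; nasal congestion and craving terms are absent too. The documents do not support requiring those additions:
- Under Protocol 6.10.2 a symptom on a scale becomes an adverse event only if it needs intervention or is judged clinically significant.
- *Muscle spasms*, *Rhinitis*, *Rhinorrhoea* and *Flushing* are already listed, and how a reported stomach cramp would be coded cannot be settled from the documents.
- In Table 2 of the label in Protocol Appendix 7, abdominal pain was 11.2% and 11.7% on the two buprenorphine products against 6.5% on placebo, while withdrawal syndrome ran the other way: 25.2% and 18.4% against 37.4%. These are small 4-week sublingual data, but they suggest that general abdominal terms would bring in events that are not withdrawal.
- COWS, SOWS and the Opioid Craving VAS measure withdrawal and craving directly (SAP 9.5.2 to 9.5.4).

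Adding those terms would trade specificity for sensitivity, and leaving them out is defensible.

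**Conclusion.** The point holds for the respiratory list: the 9.6.1.9 table can under-count. A subject is missed when three things are true together: a desaturation or hypoxia event is reported as a TEAE, it is coded outside the 31 terms, and the subject has no other listed term.

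A reader might infer that the table does under-count, or that it would show zero despite real events. The documents do not support either. They contain no rate for such events, and the first-in-human study, with 12 subjects and a single 20 mg dose, reported none. The 600 × p figures are illustrations over assumed rates, and the true number may be zero. The case for acting is that the gap is plain, it runs in one direction, it lies in a primary-safety table for a long-acting opioid, and it is cheap to close.

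**What to change.** Before final lock, add *oxygen saturation decreased*, *hypoxia* and equivalent terms to the Appendix 2 respiratory list, with exact preferred terms checked against MedDRA 17.1. In the 9.6.1.9 table, show counts for the present 31 terms and for the extended list side by side, so that the effect of the change is visible and nobody can say the list was adjusted to suit the result. Name the source query and scope in Appendix 2, so that a reader can see which terms were inherited and which were added.

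The cost is an appendix edit and one table rerun. The downside is a slightly less specific list, since low saturation has causes other than opioid effect; the side-by-side display lets a reader judge that. No change to the withdrawal list is required.
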